 4. **Expand:** Work to expand your awareness of the situation. You already are slowing down your breath, now focus on the breath to allow your body and your mind to soften. We are expanding our awareness back out to the feelings in the body, the sensations of being in the room, and allowing ourselves to be centered and grounded in this moment.
 5. **Respond:** Allow yourself to respond mindfully. How can you truly take care of yourself in this situation? What do you really need? Take a moment to choose your response – knowing that you do have a choice.
 - a. People may think of this as “wise mind” – acting with purpose and reason.
 - b. Importantly, the person might still choose the same reaction/response – that is okay. Our goal is to just be more present with our response to situations, triggers, urges. Allow the participant some time to process this part of SOBER. Encourage the participant to be empowered to make a choice and to be more present when choosing a response.

7. Wrap-Up (2 minutes)

- a. *We covered a lot today during our session. I did want to remind you that next time is actually going to be our last session together! Do you have any questions for me today?*
- b. *Let's schedule our final session together.*
- c. Provide participant with date and time of session.

Psychosocial Intervention Session 4 (38 minutes with assessments):

1. Introduction (1 minute)
 - a. Getting Permission to Record
 - b. *Hi _____, how are you today? Is this still a good time for us to do our final session together? Great! And before we get started today, do I have your permission to record this session? Wonderful, thank you!*
2. Assessment (20 minutes)
 - a. Complete session four assessment forms in FileMaker.
 - b. *Because you finished your assessment, I will mail you that \$25 gift card. Do you prefer Kroger or Walmart? Please allow 2-3 business days for it to arrive.*
 - c. *Thanks for getting the assessment completed today.*
3. Orientation to Session (1 minute)
 - a. *Today, we will discuss improving self-control. We'll also review the opioid-free activities you've been trying, and touch base on how SOBER has been working for you.*
 - b. *What questions or thoughts do you have for me before we get started?*
 - c. If the participant missed the previous session , take a few moments to inform them of the information they missed.
4. Improving Self-Control (5 minutes)
 - a. *I would like to introduce you to an activity we call "improving self-control."*
 - b. *You may not know this, but self-control changes for people during the course of recovery.*
 - c. *What do you think self-control is?*
 - i. Let participant answer.
 - ii. *Yes! We also think of it in these ways:*
 1. *The ability to identify your long-term goals and act in a way that is consistent with those goals*
 2. *The ability to wait for a bigger reward to come at a later time.*
 3. *The ability to keep working on a task or goal even if it difficult or results in frustration or set backs*
 - d. Improving Self-Control
 - i. *What are some ways you think people can improve their self-control?*
 1. *Great ideas! I have some other ideas – do you mind if I share them?*
 2. *Identify your short and long term goals*
 - a. What are your values, what is important to you in life?
 - b. Where do you want to be in 2 years? In 10 years?
 3. *Write down these goals* and consult them regularly as you decide on what you are going to do each day.
 4. *Make your goals public* (post them on Facebook, tell your friends and family)
 - a. GET SOCIAL SUPPORT
 5. *Record your progress* towards your goals (can do this with pencil and paper, on your phone, or on your computer)

6. Make specific commitments to the things you want to get done (e.g., if you want work out every morning, make a plan to do this with a friend).
 7. Use rewards for accomplishing your goals (stickers, money you put away to spend if you accomplish your goal each week, etc.).
 8. Remind yourself of the benefits of accomplishing your long term goals (e.g., a promotion, higher salary, nurturing important relationships, being healthy, etc.)
 9. Self-control is like a muscle. Self-control gets stronger with practice – it's gets easier over time to resist temptation and to stick with your healthy routines and commitments.
 - a. Also remember HALT: hungry, angry, lonely, tired. It's hard to have self-control if you are tired, grumpy, hungry, sad, etc. Get good rest, eat well, exercise, take short breaks from challenging activities, and plan fun events to keep your mood good.
 10. Identify (and avoid) high risk people and situations that get in the way of your goals
 11. *What do you think about these ideas? Would you find any of them useful? Which ones?*
5. Substance Free Activity Check In (5 minutes)
- a. *I know we've talked a lot about some activities/hobbies you've started to work on. How has it been going trying _____?*
 - i. Allow the participant a few minutes to discuss the opioid-free activities.
 - b. Focus the conversation on problem-solving any barriers that have come up for them with their new activity/hobby.
 - c. *I have one more tip to offer you as you continue to fill your time with new opioid free activities. It's always helpful to have a calendar or use your phone to schedule your plans. This will be helpful to increase your awareness of what's on your schedule and the activities you have to look forward to!*
 - d. *What other questions do you have about your new opioid-free activities?*
6. Mindfulness-Based Adherence Promotion Check In (5 minutes)
- a. *Tell me a little bit about your experiences in using the SOBER breathing space.*
 - b. Take some time to complete one final review of SOBER and problem-solve ways to help the participant use this in daily life.
 - c. *SOBER stands for:*
 - i. **Stop** and see what happens
 - ii. **Observe** physical sensations and emotion regulation changes in the body
 - iii. **Breathe** by deliberately bringing attention to the breath
 - iv. **Expand** awareness of the situation
 - v. **Respond** mindfully (versus reacting)
 - d. *We've gone over how to use the SOBER breathing space when experiencing cravings, urges, and triggers. How do you think you will continue to use this skill to support your recovery?*
7. Wrap-Up (1 minute)
- a. *We have covered a lot of things during our sessions together over the past few months. What questions do you have for me?*

- b. Allow the participant to process any last-minute concerns or questions. Thank the participant for their time in the study.

Participants will also receive a copy of the “Tips for Improving Self Control Handout” located on OneDrive.

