8.6. Intervention Sessions

Prior to the session, Interventionists will prepare for the brief assessment conducted during each treatment session by finding the participant in the Filemaker database, or if offline, entering the participant information on the top of the assessment materials.

Interventionists will also prepare to administer the appropriate session (1, 2, 3, or 4) (within the appropriate condition).

In addition, Interventionists will prepare the recording device to ensure that the session is recorded. If remote, the interventionist will text or email the participant a Zoom telephone number with a meeting ID for them to call and be placed in a meeting. The interventionist will ensure that Zoom is recording once permission is granted from participant. All sessions will be recorded and uploaded to OneDrive folder (SMART Project 3/Recordings) and labeled with the participant's study ID, session number (1, 2, 3, 4), condition (CM vs. BSM), and staff initials. (e.g. 301 S2 BSM AB)

At each session , the Interventionist will meet with the participant to complete the assessment questionnaires and complete the intervention – either a BSM session or a wheel spin for additional gift cards for CM (if requirements are met).

If the participant drops out of treatment at the Center for Addiction Science, they will no longer receive the CM or BSM. However, all assessments will be conducted regardless of the participant's adherence to medical treatment at the CAS. Upon completion of the assessment, participants will still earn the \$50 gift card. This will allow us to understand the reason for the participant's non-adherence to treatment, and to evaluate whether these individuals pursue treatment elsewhere.

The intervention scripts are available in section 13 of the manual of procedures.

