8.8.2. Gift Card Distribution

All gift cards will be pre-purchased, hard copy gift cards.

Baseline Assessment Incentive: All participants will receive a \$50 gift card for enrolling and completing a baseline visit.

Assessment Completion Incentive: After each assessment, participants will receive a \$50 gift card to their choice of store (Kroger or Walmart). Research staff will log out the gift card(s), make a photocopy of the gift card(s), and have the participant sign the photocopy to document distribution. Research staff will date the photocopy and file appropriately.

CM Group Rewards: Patients in the CM arm will have the opportunity to spin a computer number wheel if it is determined that buprenorphine is in their urine at the physician visit. If all 4 urine screens across the study duration show buprenorphine in urine, the participant will receive a \$100 bonus gift card.

This is allowed by UT policy FI0313.

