8.12. Participant Retention for Enrolled Participants

If a participant is having difficulty participating in sessions regularly, it is the job of the Interventionist to find out obstacles to treatment and work with the participant to overcome these obstacles.

Once a participant is enrolled, it is the Interventionist's goal is to retain them in the study.

In addition to FileMaker, Interventionists should regularly update the Retention Log in OneDrive with their active participants. Interventionists have the flexibility to provide participants whatever form of treatment is needed to retain them in the study. Before offering participants special arrangements, Interventionists will review these cases with the Study Team.

Procedures are in place to assist you in retaining participants. These include incentives for assessments (\$50 gift cards), as well a t-shirt and welcome bag (snacks and cloth face mask) that will be provided at enrollment.

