If the participant does not want to continue participating in phone sessions, emphasize to them the importance of completing the assessments. Ask the participant if he/she is willing to complete these measures. The participant would be considered inactive and would still receive the \$50 gift card if the session is completed (S1, S2, S3, or S4). Emphasize that their data is needed for the success of the research, whether or not they have been actively participating or not and whether or not they've quit. In order to answer the research questions, we need to know what worked and what DID NOT work for

participants so we can help others better in the future. Explain that without their data, we will be missing some of the most crucial information we need to collect.

Participants who do not complete the Baseline assessment within the designated window will be administratively withdrawn from the study since they did not complete any treatment.

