12. CM INTERVENTION SCRIPT

Hi _____. Nice to see you again. As you may remember, we check on your toxicology results to determine whether you are eligible for the number wheel.

Buprenorphine Present:

I see today you do have medication in your system. Congratulations! You are eligible for the wheel spin. As a reminder, the wheel includes gift cards ranging from \$25 to \$100. You will spin and land on a random number.

<https://pickerwheel.com/>

Buprenorphine Not Present:

I see today you do not have medication in your system. I'm sorry, but you will not be eligible for the wheel spin today.

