13. BSM INTERVENTION SCRIPT

Psychosocial Intervention Session 1 (40 minutes with assessments):

Session Prep:

- a. Ensure participant has received SOBER Handout at baseline
- b. Print off blank Goals worksheet for Session 1 to fill out during session
- c. Participant should have completed the “Time Spent on Activities Worksheet” at baseline.
 - i. Have a graph of the time spent in each activity prepared and sent to the participant before the session begins
- d. Print off blank Future Event Description worksheet for Session 1 (Goals, Future Event Description) to fill out during session

1. Introduction (2 minutes)

a. Getting Permission to Record

- i. *Hi _____, is this still a good time for us to do our first session together? Great!*
- ii. *Before we get started today, I wanted to let you know all of our sessions will be recorded for the purpose of the study.*
- iii. *Do I have your permission to record this session? Thank you so much.*

b. Mandated reporting

- i. *Also, I wanted to let you know that I am a mandated reporter. That means if you let me know about any ongoing abuse, either to yourself or to someone else, or if you inform me of any intentions to harm yourself or someone else, I am obligated by law to report that. If anything like that comes up during any of our sessions, I would let you know ahead of time.*
- ii. *Do you have any questions about that?*

2. Assessment (10 minutes)

- a. Complete session one assessment forms in FileMaker.
- b. *Thank you for taking the time to answer all those questions.*
- c. *Because you finished your assessment, I will mail you that \$25 gift card. Do you prefer Kroger or Walmart? Great!*
- d. *Please allow 2-3 business days for it to arrive. If there are any issues, please don't hesitate to reach out!*

3. Build Rapport (1 minutes)

- a. *So I'd like to get to know a little more about who you are. Tell me who are the most important people in your life and one or two things you like to do – just a minute's worth of who you are.*
 - i. Wait for participant to tell you about themselves – MAXIMUM 1 minute

4. Orientation to Session (1 minute)

- a. *Thank you for telling me about yourself.*
- b. *Let me tell you about what we will be doing with our time together.*
 - i. *My overall goal is to support your treatment at the Center for Addiction Science and help you meet your goals.*

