14. VIRTUAL MAILING PROCEDURES

Session /Mailing Procedures:

Baseline

- If participant completes the full package in-person, they will receive a \$50 gift card before they leave the clinic.
 - Each interventionist is responsible for taking care of their own gift cards and welcome package (T-shirt, copy of consent, SOBER handout [BSM group only], and business card).

Instructions:

- Log gift cards out of the safe.
- Complete the GC sheet and make copy of gift card for study records.
 - Ppt. will need to sign off on the sheet. Once completed place in GC binder.
- Present GC to ppt
- Welcome ppt. to the study and hand them their welcome bag.
- Schedule next session (based on their appt. with clinic).

- If the participant takes the packet home, they will need to return the package back or call to complete the assessment over the phone. Once completed, we will mail them a \$50 gift card; if they come back into the clinic, we will give them a gift card in person.
 - Each interventionist is responsible for taking care of their own gift cards and welcome package (T-shirt, copy of consent, SOBER handout [BSM group only], and business card).

Instructions:

- Schedule a time to complete baseline.
 - Inform the ppt. that we will not be able to mail GC without completing the pack first.
- Welcome ppt. to the study and hand them their welcome bag.
 - T-shirt, copy of consent, SOBER handout [BSM group only], and contact card.
 - No GC will be given until pack is completed.

Once baseline is completed:

- Log gift cards out of the safe.
- Complete the GC sheet and make copy of gift card for study records.
 - Once completed place sheet in GC binder (ppt. will not need to sign).
- Mail GC to ppt.

- Mail can be dropped off at the UCH lobby or nearest postal office.
- Use SMART mailer and envelop.

Sessions 1-3 (Virtual)

- After the participant completes all the assessments and the intervention, they will receive their GC. Appointments will be scheduled within 30 day windows.

- **CM Group Instructions:**

- Complete assessments
- Inform ppt. of the GC amount they will receive, and to please allow 2-3 business days to arrive.
 - \$50 for completing assessments.
 - Additional GC will depend on the following:

Urine toxicology results

- If participant is compliant, buprenorphine in their urine, we will spin the virtual wheel for them and inform them of the amount received.

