- If participant is not compliant, no buprenorphine in their urine, we will inform them that they will not be able to participate in the number wheel at this time.

- Study team will take a screenshot of the number wheel and will text or email ppt. the results; only when applicable.

- Place ppt. ID and GC amounts in the GC google sheet for future mailing.
 - Study staff that is present in the clinic will be responsible for GC mailings for that day.
 - If no staff is available that day, please inform the ppt. that they will receive GC in X number of days (based on when staff will be in clinic next).
- Mail GC to ppt.
 - Mail can be dropped off at the UCH lobby or nearest postal office.
 - Use SMART mailer and envelop.

- **BSM Group Instructions:**

- Complete assessments and intervention.
- Inform ppt. of the GC amount they will receive (\$50), and to please allow 2-3 business days to arrive.
- Place ppt. ID and GC amounts in the GC google sheet for future mailing.

- Study staff that is present in the clinic will be responsible for GC mailings for that day.
- If no staff is available that day, please inform the ppt. that they will receive GC in X number of days (based on when staff will be in clinic next).
- Mail GC to ppt.
 - Mail can be dropped off at the UCH lobby or nearest postal office.
 - Use SMART mailer and envelop.

Note: If study team does not have access to postage stamps, Wednesdays and Fridays will be designed gift card mailing days. Study team will alternate days that they deliver gift cards to the UTHSC main campus.

- Wednesdays: Red bag will be dropped off at the Pauline bldg.
- Fridays: Study team will take the red bag to the mail room in the Madison bldg.

Instructions:

- Use the GC google sheet to confirm gift cards that need to be mailed.
- Log gift cards out of the safe.
- Complete the GC sheet and make copy of gift card for study records.
- Once completed place sheet in GC binder (ppt. will not need to sign).
- Place GC in red bag and take to designed mailing area for that day.
 - Use SMART mailer and envelop.
- Log mileage from clinic to the main office and submit monthly.

Session 4 (Virtual): Part 1

- After the participant completes Part 1 of the assessments and the intervention, they will schedule Part 2 of the session .

Instructions:

- Complete Part 1 assessments
- Complete the intervention
- Schedule follow-up call with the RA.

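### All four BSM session scripts promise a $25 card for the assessment, while every payment rule, including BSM's own mailing instructions, sets $50

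*Protocol*

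**What the plan says.** The assessment step of all four BSM scripts (protocol section 13) has the counselor say: "Because you finished your assessment, I will mail you that \$25 gift card".

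The payment rules give a different amount:

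- Section 8.8.2, for all participants: "After each assessment, participants will receive a \$50 gift card to their choice of store (Kroger or Walmart".
- Section 8.6, Intervention Sessions, for those who leave clinic treatment: "Upon completion of the assessment, participants will still earn the \$50 gift card".
- Section 8.12, on retention measures: "These include incentives for assessments (\$50 gift cards".
- Section 18.13.3, for participants who become inactive: "would still receive the \$50 gift card if the session is completed (S1, S2, S3, or S4".
- Section 14, CM instructions for virtual Sessions 1 to 3, where the amount line reads, after the dollar sign: "50 for completing assessments".
- Section 14, BSM instructions for the same sessions: "Inform ppt. of the GC amount they will receive (\$50), and to please allow 2-3 business days to arrive".

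The CM script (section 12, CM Intervention Script) names no assessment payment. There, $25 appears only as the lowest wheel prize: "As a reminder, the wheel includes gift cards ranging from \$25 to \$100".

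**The concern.** The assessment card is the payment that does not depend on adherence, and no rule makes it differ by arm. By the plan's own rules, the money should differ only through the CM wheel and bonus. A spoken figure of $25 in BSM alone puts a second, unplanned difference between the arms.

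The line is likely to be read out. Section 3.1 makes the manual the official reference and asks staff to follow it closely, and section 5.4 plans content fidelity checks on 40 of 80 recorded sessions. The same interventionists deliver both arms (section 4.3.4).

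Retention is part of the feasibility definition in section 3.2. Feasibility and satisfaction are both primary outcomes in section 3.3. Satisfaction is collected in the blinded call shortly after Session 4 Part 1, so in BSM the last $25 statement comes just before it. Participants should also be told the correct payment, whether or not any bias follows.

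**Working it through.** The $50 is a set amount, so there is no derivation to reproduce. The check is a comparison of texts with simple arithmetic.

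**1. What each text tells staff about the assessment card**

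| Text | BSM | CM |
|---|---|---|
| Session script | $25, Sessions 1 to 4 | no amount |
| Section 14, virtual Sessions 1 to 3 | $50 | $50 |
| Section 14, virtual Session 4 | no amount; card only after all parts | no amount; card only after all parts |
| Sections 8.6, 8.8.2, 8.12, 18.13.3 | $50 | $50 |

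Only the script row differs by arm. The script and the BSM mailing instructions cover the same event: both concern a card sent by mail and both quote the same delivery time. A BSM counselor is thus told to name two amounts for one card.

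**2. Size of the discrepancy**

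- Per session: $25 / $50 = 0.50, a gap of $25.
- Four sessions: 4 x $25 = $100 as scripted, against 4 x $50 = $200 under the rules, a gap of $100.
- With the $50 baseline card (section 8.8.2): $100 + $50 = $150, against $200 + $50 = $250.
- With the scripts set to $50, both arms come to $250.

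These are announced amounts. Wheel prizes and the bonus are separate and not counted.

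**3. When the statement can act**

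The sentence follows the completed assessment, so it cannot change whether that assessment is done. The Session 1 statement can influence Sessions 2 to 4 and the Part 2 call. The Session 4 statement can influence only Part 2.

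**4. Which data could be affected (Table 1, section 12.1)**

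- Blinded call: satisfaction, delay discounting, engagement in substance-free activities, EQ-5D-5L.
- Sessions: opioid purchase task, timeline followback, craving and the other self-reports.
- Adherence as the protocol defines it, attendance plus buprenorphine in urine, comes from clinic records (sections 3.4.4, 3.6.2 and 3.6.4). A missed questionnaire does not remove these data.

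The SAP expects BSM to do better on substance-free activities, delay discounting and opioid demand. These rest on the participant-completed measures. With 20 per arm (section 3.5), one BSM participant lost from such a measure is 1/20 = 5 percentage points of that arm.

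**5. Session 4**

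The Session 4 script promises the card on completion of its own assessment. The Session 4 note in section 14 withholds the card until the Part 1 and Part 2 assessments and the intervention are all complete. Changing the amount alone would leave this second conflict.

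**The case against.** The strongest reply is that the arms are treated equally where like is compared with like. The CM script states no amount, so the CM $50 has to come from section 14 or the general rules, and section 14 tells BSM staff to name $50 too. Cards are logged and photocopied, and no payment rule authorizes $25. On this view the scripts are simply out of step with a rule stated consistently elsewhere, in a 40-person pilot meant to give feasibility, satisfaction and preliminary effect sizes.

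Most of that stands, and it rules out three stronger readings:

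- **A reader might infer that BSM participants are paid half of what CM participants receive.** The documents do not show this. They show a conflict within the BSM instructions, and the mailed amount may well be $50.
- **A reader might infer bias in the adherence comparison toward CM.** The card is paid whether or not the participant attends the clinic (sections 8.2.1, 8.6 and 8.10), and the adherence data come from charts. An effect on attendance through sessions scheduled around clinic visits is conceivable, but it is indirect and nothing in the documents allows it to be sized.
- **A reader might treat the card as the trial's principal retention measure.** Section 8.12 lists it with a t-shirt and welcome bag, and sections 8.12.1 to 8.13.2 describe extensive contact efforts.

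The reply does not remove the contradiction. The $25 stands in four scripts that staff are asked to follow, in one arm only. If staff say $25 and mail $50, the BSM participant has still been given a wrong figure.

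**Conclusion.** The inconsistency is real and should be fixed. Read as written, the scripts announce half the stated payment to BSM participants: $25 less per session, $100 less over four sessions. No text gives CM a lower figure. The consequence depends on counselors reading the line as scripted and on participants taking note of it. The documents do not say how often either happens, so no bias can be quantified. The outcomes exposed are later assessment completion, the Part 2 call, retention, satisfaction and self-reported measures. The design, the analysis and the chart-based adherence data are not touched. That $50 is the intended amount rests on its consistent use in every payment rule. The consent form is not in the documents reviewed, so this needs confirming.

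**What to change.** 1. Confirm the assessment payment against the approved consent form.
2. If it is $50, as section 8.8.2 states, change $25 to $50 in the assessment step of the Session 1, 2, 3 and 4 BSM scripts.
3. Add the same assessment-payment sentence to the CM script, so that both arms hear identical words.
4. Reword the Session 4 line so that it agrees with section 14 on when the card is given.
5. Review the gift-card logs and session recordings, by arm, for anyone told or paid $25. Record these as deviations and correct any underpayment against the confirmed amount.

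The cost is four corrected lines, one added sentence and a check of records the study already keeps. It should be done before the scripts are used further or carried into Project 4.

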3.4.3. Final Assessment (Participant)

All participants will complete a blinded treatment satisfaction follow-up assessment shortly after completing Session 4 Part 1. Session 4 Part 2 assessment is to be conducted by an assessor blind to study conditions.

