 - RA will be responsible for logging ppt. ID, completion date, and GC amount in the google sheet and notifying team of completion status.
 - Note: Ppt. will not receive GC unless they complete all parts of the session (Part 1 & 2 Assessments and intervention).

Session 4 (Virtual): Part 2

To be completed by RA.

- Complete Part 2 assessments and log session info. in the google sheet for future GC mailing.

Instructions:

- **Complete Part 2 assessments**
- **Complete treatment satisfaction survey**
- **Notify team of completion (via email or GroupMe msg.).**
- **Log study ID, date of completion, and GC amount in the google sheet**
- **Mailing will be the same as Sessions 1-3.**

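### The BSM Session 4 script contradicts the two-part Session 4 procedure, so the blinded Part 2 measures could be missed or collected unblinded

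*Protocol*

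**What the plan says.** **The two-part procedure.** Protocol section 3.4.3 splits the last session: "Session 4 Part 2 assessment is to be conducted by an assessor blind to study conditions". Section 3.6.3 gives that follow-up call to a blinded research assistant and allows 25 minutes. Section 14, under Session 4 (Virtual), has staff complete Part 1 and the intervention, then "Schedule follow-up call with the RA". It adds the payment condition: "Ppt. will not receive GC unless they complete all parts of the session (Part 1 & 2 Assessments and intervention").

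**The script.** The BSM Session 4 script in section 13 is headed "Psychosocial Intervention Session 4 (38 minutes with assessments"). Step 2 is "Assessment (20 minutes"), with the instruction "Complete session four assessment forms in FileMaker". The counselor then says "Because you finished your assessment, I will mail you that" gift card, and thanks the participant for having completed the assessment. The wrap-up ends with "Thank the participant for their time in the study". The script mentions neither Part 2, nor a research assistant, nor any condition on the card.

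**Other card rules.** Section 8.6 (Intervention Sessions) and section 8.8.2 tie the card to completing the assessment, in both arms. Section 8.6 keeps that entitlement for participants who have left clinic treatment and no longer receive the intervention.

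**What Part 2 collects.** In Table 1 (section 12.1), treatment satisfaction is marked only in the 8-week blind column. Delay discounting, engagement in substance-free activities and EQ-5D-5L are marked only there and at baseline. Section 3.3 makes satisfaction a primary outcome, and the SAP names reduced delay discounting as an expected BSM benefit.

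**The concern.** A counselor who follows the script tells the participant that the assessment is over and the card is on its way, and ends the contact without booking the call. Two things can then go wrong.

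- **Missed Part 2.** The participant has been given no appointment and has less reason to take a further call. Each participant who misses it loses the only post-randomization value of four measures.
- **Lost blinding.** If the counselor reads the longer assessment step as including the Part 2 set, participants rate the person who delivered the material while speaking to that person. Sections 3.4.3 and 3.6.3 are meant to prevent this.

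The premature close is scripted for BSM alone, so either problem could fall unevenly on a comparison planned with 20 participants per arm. The payment rule is a linked problem for both arms. Read literally, section 14 denies the Session 4 card to anyone who did not receive the intervention, whereas section 8.6 promises it to treatment dropouts who complete the assessment.

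**Working it through.** **1. Is the 20 minutes a slip?** The Session 4 step times sum to 1 + 20 + 1 + 5 + 5 + 5 + 1 = 38, the total in the heading. The other BSM scripts also reproduce their stated totals:

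- Session 1: 2 + 10 + 1 + 1 + 5 + 5 + 10 + 5 + 1 = 40
- Session 2: 1 + 10 + 2 + 1 + 5 + 7 + 7 + 5 + 1 = 39
- Session 3: 1 + 10 + 2 + 1 + 5 + 20 + 2 = 41

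Sessions 1 to 3 allow 10 minutes for assessment, as section 3.6.2 does. Session 4 allows twice that, and the 20 minutes is built into its total.

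**2. What could the 20 minutes contain?** Table 1 totals are 11 minutes for the session set and 10 for the blind set, so 11 + 10 = 21, close to 20. Against that, the four blind items sum to 2 + 2 + 4 + 3 = 11, not 10, and section 3.6.3 gives the call 25 minutes, which with a 10-minute session set makes 35. The figures permit the reading that the counselor covers both sets but do not establish it.

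**3. Side by side.**

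| Element | Sections 3.4.3, 3.6.3, 14 | BSM Session 4 script |
|---|---|---|
| Structure | Part 1, then Part 2 | One assessment step |
| Who assesses | Interventionist, then blinded assistant | Counselor |
| Card | After both parts and the intervention (section 14 only) | Promised straight after the assessment step |
| Close | Book the call | Thanks, no booking |

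The wrap-ups of Sessions 1 to 3 each script the next booking. Session 4, which should lead to the blinded call, does not.

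**4. Length after correction.** With Part 1 only, the script totals 38 − 20 + 10 = 28 minutes (section 3.6.2) or 38 − 20 + 11 = 29 (Table 1).

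**5. Illustration of size.** The documents give no completion rate for Part 2, so every rate below is an assumption.

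- *Precision, 18 of 20 CM completers.* The ratio of the standard error of the arm difference to that with 18 per arm is sqrt[(1/18 + 1/n) / (2/18)]. For n = 16, 14 and 12 in BSM it is 1.03, 1.07 and 1.12.
- *Precision, all 20 CM completers.* The 95% half-width in SD units is 1.96 × sqrt(1/20 + 1/n). For n = 20, 18, 16, 14 and 10 in BSM it is 0.62, 0.64, 0.66, 0.68 and 0.76.
- *Bias.* Let non-completers in both arms score d points lower than completers. The complete-case difference (BSM minus CM) is then shifted by d × (BSM missing fraction − CM missing fraction). With d = 1 and a CM missing fraction of 0.1, BSM fractions of 0.2, 0.3 and 0.4 give 0.1, 0.2 and 0.3 points in favor of BSM. With d = 0 the shift is zero, and with d negative it changes sign.

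**The case against.** The correct procedure is already written. Section 14 tells staff in both arms to book the call and assigns Part 2 to the research assistant, and sections 3.4.3 and 3.6.3 agree. The same interventionists deliver both arms (section 4.3.4). Section 8.5 asks staff to keep trying to assess after the Session 4 window closes, and sections 8.13.1 and 8.13.2 require repeated contact while a window is open. The card sentence recurs in all four BSM scripts and looks like text that was not updated. Adherence comes from charts and is untouched. All of this stands, and it makes loss a risk rather than a certainty. It does not remove the conflict: section 3.1 makes the manual the official reference, section 8.6 points interventionists to the scripts, and section 5.4 has half the sessions checked for content.

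Four stronger readings are tempting, but the documents do not support them:

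- **The conflict is confined to BSM.** The CM script also omits Part 2, and the payment rules conflict for both arms. Only the completion statement, the early card promise and the study close are specific to BSM.
- **Section 3.4.3 makes payment depend on Part 2.** It says nothing about payment; that rule is only in section 14, under a virtual-session heading. The script also speaks of mailing the card, so the two texts do meet in the remote setting.
- **The counselor is meant to collect Part 2.** That is an inference from 20 being near 21. Sections 3.4.3, 3.6.3 and 14 say otherwise, and the 25-minute call does not fit it.
- **The arm comparison is biased.** Participants who skip the call because they were told they had finished need not differ in satisfaction, and if they do not, these extra losses add no bias.

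**Conclusion.** The contradiction is real and stands in the current text. The BSM Session 4 script and the two-part procedure cannot both be followed as written, and the section 14 card rule also disagrees with sections 8.6 and 8.8.2 in both arms. At risk is the sole post-randomization value of satisfaction, delay discounting, substance-free activities and EQ-5D-5L, through missed calls or unblinded collection, possibly to a different degree in each arm.

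The size and direction of any bias cannot be derived from the documents. The 3% to 12% loss of precision rests on assumed completion of 18 of 20 in CM and 16 to 12 of 20 in BSM. The 0.1 to 0.3 point shift also needs the assumed 1-point deficit in non-completers. Both are illustrations only. The precision cost is modest for a 40-person pilot whose SAP puts less weight on significance testing. The case for correction rests on protecting a primary outcome and its blinding at almost no cost.

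**What to change.** In the BSM Session 4 script:

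1. Label step 2 as the Part 1 assessment, set its time to match section 3.6.2 or Table 1, and correct the 38-minute total (28 or 29). State that the measures in the 8-week blind column are collected only by the blinded research assistant.
2. Replace the card statement with one that matches the reconciled payment rule: under section 14, the card is sent after the Part 2 call. Align sections 8.6 (Intervention Sessions) and 8.8.2 with it, and say how the rule applies to participants who no longer receive the intervention.
3. Add to the wrap-up a line booking the Part 2 call with the research assistant.

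Add the same Session 4 closing and booking line to the CM script, so that both arms hear the same thing.

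The cost is a few lines in two scripts and a wording change in the card sections. No visit, staff member or measure is added.
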